9 ASSESSMENT OF INVESTIGATIONAL MEDICINAL PRODUCT

9.1 PRIMARY ENDPOINT

9.1.1 Primary efficacy endpoint

Pulmonary function testing (PFT) will be performed locally at the time points specified in [Section 1.2](#) and measured by a central laboratory. During the treatment period, the assessment will be completed before IMP infusion. Assessment should continue to be collected for at least up to Week 49, end of PAP, if the patient discontinues the treatment earlier.

The PFT administration protocol is standardized across sites in accordance with ATS/ERS guidelines (2). Per ATS/ERS 2005 quality standards, an adequate test requires a minimum of 3 acceptable FVC maneuvers and acceptable repeatability needs to be met for the largest and next-largest FVC and forced expiratory volume in the 1st second of the FVC maneuver (FEV₁) as outlined in the study manual. Patients may repeat the PFT assessment up to 3 times within the Screening Visit time window in case of failed quality as determined by the central laboratory (refer to [Section 7](#) for details on screening and re-screening conditions). For each PFT assessment, up to 8 efforts may be performed. Patients are not allowed to use noninvasive ventilation during this assessment. The primary efficacy endpoint is the change from baseline to Week 49 in FVC (% predicted) in upright position. FVC will be reported in liters and percent of predicted normal values based on age, gender, race, and height. Global Lung Initiative (GLI) 2012 reference equations will be used for this study (3).

Postbaseline PFT should meet the ATS/ERS 2005 quality standards. However, if no acceptable efforts can be recorded during the upright position PFT with up to 8 efforts, an additional PFT may be scheduled as soon as possible no later than 45 days after this failed planned test, if this is feasible for the patient. The highest acceptable effort will be kept in the database.

In addition, if the patient did not perform the PFT at a planned visit, the patient should be reminded to perform the PFT as soon as possible no later than 45 days after the missed test, if it is feasible for patient to perform the test within this period.

Refer to the study specific manual for instructions on test administration.

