Patients will be required to remain in the hospital or the infusion center for observation of AEs for 1 hour after each infusion; see below for the patients receiving home infusion. Patients may be required to stay for a longer observation period at the Investigator's discretion. In case the patient does not stay for this observation period (eg, as part of contingency measures for a regional or national emergency that is declared by a governmental agency), the Investigator (or appropriate designee) will contact the patient or their legally authorized representative (for pediatric patients) to ensure that no adverse event occurred during the observational period.

The study includes 2 main periods: the blinded treatment period and the open-label avalglucosidase alfa long-term follow-up phase.

In the blinded treatment period avalglucosidase alfa or alglucosidase alfa will be administered by IV infusion every 2 weeks starting at Randomization Visit (Visit 2, Day 1/Day 2) continuing up to V27/W49 for a total of 25 doses.

Patients in the alglucosidase alfa arm will be switched to avalglucosidase alfa treatment after 12 months.

In the open-label avalglucosidase alfa long-term follow-up phase, avalglucosidase alfa will be administered by IV infusion every 2 weeks starting at V28/W51 continuing up to V76/W145 for a total of 48 doses.

In the extended open-label avalglucosidase alfa extension period, avalglucosidase alfa will be administered by IV infusion every 2 weeks starting at V77/W147 and continuing up to 144 additional weeks (or until avalglucosidase alfa is approved in the patient's country, whichever comes first; refer to Appendix C [Section 17.3.3](#) for patients in Canada and [Section 17.3.4](#) for definition applicable for UK patients) for up to 72 additional doses.

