10.1.3 Blinded treatment period

Patients enrolled in the study will have the following procedures performed starting at Day of first infusion. Day of first infusion should occur within 1 to 14 days after Screening/Baseline. All subsequent visits are calculated from day of first infusion of IMP in 14-day increments with a window of ± 7 days for infusions and safety assessments and ± 14 days for all other assessments.

A patient card will be provided to the patient once the patient is randomized (see study manual for details).

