 - If efficacy assessments/procedures should have been performed during that missed visit (ie, V9/Week 13, V15/Week 25, V21/Week 37, V27/Week 49, V34/Week 61, V40/Week 73, V52/Week 97, V64/Week 121 [not applicable for pediatric patients aged 3 to <18 directly enrolled in the open-label long-term follow-up phase], V76/Week 145 [not applicable for pediatric patients aged 3 to <18 directly enrolled in the open-label long-term follow-up phase], or any every 24 weeks visit of the extended open-label long-term follow-up phase), they will be performed at the earliest possible date (which might exceed the authorized window) and will still be associated with the visit that was missed (see CRF completion guidelines for details regarding the CRF completion in this case). In these instances, this will not be considered a deviation but should be clearly documented in the patient's file. Refer to [Section 9.1.1](#) for details on PFT when missed.
- Visits that are longer due to multiple assessments or procedures (eg, motor assessments and multiple questionnaires) may be carried out over 2 days. In any case, IMP

administration should be the last procedure and the appropriate time needed for post-infusion surveillance will be taken into account.

- Postbaseline PFT should meet the ATS/ERS 2005 quality standards. However, if no acceptable efforts can be recorded during the upright position PFT with up to 8 efforts, an additional PFT may be scheduled as soon as possible no later than 45 days after this failed planned test, if this is feasible for the patient. The highest acceptable effort will be kept in the database.
- In addition, if the patient did not perform the PFT at a planned visit, the patient should be reminded to perform the PFT test as soon as possible no later than 45 days after the missed test, if it is feasible for the patient to perform the test within this period.

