2.10.5 Windows for time points

The visit windows for efficacy endpoints specified in [Table 16](#) are defined in following table. For analysis purpose, a larger window (as shown in the last column of [Table 14](#)) will be used. This will be applicable for those analyses requiring visit information.

Table 14 - Study visit nominal visit days and windows for efficacy endpoints

Scheduled Visit	Visit window defined in protocol in study days	Visit window for analysis purpose in study days
Screening/Baseline	Day -14 to -1	(-28, the day before 1st infusion)
Week 13	Day 85 ±14	(the day after 1st infusion, Day 85 +41)
Week 25	Day 169 ±14	Day 169 (-42, +41)
Week 37	Day 253 ±14	Day 253 (-42, +41)
Week 49	Day 337 ±14	(Day 337 -42, the day prior to the 1st ETP treatment or Day 337 + 41 if 1st ETP treatment is missing)
Week 61	Day 421 ±14	(the day after the 1st ETP treatment, Day 421 +41)
Week 73	Day 505 ±14	Day 505 (- 42, +83)
Week 97	Day 673 ±14	Day 673 (-84, +83)
Week 121	Day 841 ±14	Day 841 (-84, +83)

Scheduled Visit	Visit window defined in protocol in study days	Visit window for analysis purpose in study days
Week 145	Day 1009 ±14	Day 1009 (-84, +83)
Week 169	Day 1177 ±14	Day 1177 (-84, +83)
Week 193	Day 1345 ±14	Day 1345 (-84, +83)
Week 217	Day 1513 ±14	Day 1513 (-84, +83)
Week 241	Day 1681 ±14	Day 1681 (-84, +83)
Week 265	Day 1849 ±14	Day 1849 (-84, +83)

The analysis visit will be defined by comparing the actual visit date with the nominal (or target) date and the corresponding analysis window from [Table 14](#) . If more than one non-missing values are assigned to the same visit, then the one closest to the target date will be used in the by-visit analysis. Multiple values on the same date will be averaged first. If two assessments are on different date but equal distance from the target date, the later date will be used.

For the safety analyses (laboratory, ECG and vital signs), the nominal visit will be used for the by-visit type of analyses.

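### A failed or missed Week 49 FVC may be made up for 45 days, but only about 13 of those days give a usable Week 49 value, and for later tests the protocol and SAP disagree on the visit

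*Protocol*

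**What the plan says.** **Make-up rule.** Protocol 9.1.1, repeated in 10.1.8, covers two cases. If no effort is acceptable, "an additional PFT may be scheduled as soon as possible no later than 45 days after this failed planned test". If the test was not done, the patient is reminded to "perform the PFT as soon as possible no later than 45 days after the missed test". Both apply to every post-baseline visit.

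**Visit label.** Protocol 10.1.8 lists V27/Week 49 among the efficacy visits whose missed assessments are done at the earliest possible date, outside the window if need be, "and will still be associated with the visit that was missed". It does not count this as a deviation.

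**Switch.** Under Protocol 8.1, "Patients in the alglucosidase alfa arm will be switched to avalglucosidase alfa treatment after 12 months", and "avalglucosidase alfa will be administered by IV infusion every 2 weeks starting at V28/W51". Protocol 10.1.3 sets the calendar: "All subsequent visits are calculated from day of first infusion of IMP in 14-day increments with a window of" 7 days either side for infusions and 14 days either side for efficacy tests.

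**Analysis window.** SAP 2.10.5 assigns the analysis visit by actual date. In Table 14 the Week 49 window runs from Day 295 (337 - 42) to "the day prior to the 1st ETP treatment or Day 337 + 41 if 1st ETP treatment is missing". The Week 61 window opens the day after that first infusion.

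**The concern.** Week 49 is the primary endpoint visit and the only efficacy visit in the blinded period that is followed by a change of drug in one arm. The make-up rule does not recognise this. It is the same 45 days as at Weeks 13, 25 and 37, while the gap to the first open-label infusion is nominally 14 days. The instruction in 9.1.1 to test before the infusion does not help. A make-up on Day 360 precedes the Day 365 infusion but follows the one on Day 351.

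A site can therefore follow the protocol exactly, test within 45 days, label the result Week 49, and produce a value that the SAP does not accept as Week 49. That patient has no valid Week 49 FVC, which has these effects:

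- exclusion from the per-protocol set (SAP 2.3.1.2);
- non-responder status in the FVC responder analysis (SAP 2.5.3.4.1);
- in the rank-test sensitivity analysis, the worse of baseline and the last value in the primary analysis period (SAP 2.5.3.2).

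The 10% missing-data allowance was set partly to keep power in the per-protocol analysis (SAP 1.3.3). An avoidable loss eats into it.

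The same timing gap affects the other Week 49 efficacy tests. MIP and MEP belong to the lung-function test and share its 45-day limit. 6MWT and HHD make-ups have no day limit in 10.1.8.

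**Working it through.** **1. Calendar.** Week w is Day 1 + 7(w - 1).

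- Week 49 = Day 337; efficacy window (14 days either side) = Days 323 to 351.
- Week 51 = Day 351; infusion window (7 days either side) = Days 344 to 358.
- The two ordinary windows already overlap on Days 344 to 351.
- Make-up limit for a test due on Day 337 = 337 + 45 = Day 382. On the nominal schedule three open-label infusions (Days 351, 365, 379) have been given by then.

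**2. Split of the 45 make-up days (Days 338 to 382), test due on Day 337.** Let D be the day of the first open-label infusion. Days before it = D - 338. Days strictly after it = 382 - D.

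| First open-label infusion | Before it: Week 49 in the SAP | Infusion day | After it: Week 61 in the SAP |
|---|---|---|---|
| Day 344 | 6 | 1 | 38 |
| Day 351 (nominal) | 13 | 1 | 31 |
| Day 358 | 20 | 1 | 24 |

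The infusion day itself lies in neither Table 14 window.

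**3. Patients with no open-label infusion.** Table 14 ends Week 49 at 337 + 41 = Day 378. A make-up on Days 379 to 382 is inside the 45-day rule but outside the analysis window.

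**4. The plan's own sample size.** Inputs from Protocol 11.1: SD 5.1, true difference 2.0, margin 1.1, two-sided 5%, 10% missing.

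- n per arm = 2 × (1.960 + 0.842)² × 5.1² / (2.0 + 1.1)² = 42.5, so 43. Then 43 / 0.9 = 47.8, so 48 per arm and N = 96, as stated.
- Noncentral t with 43 per arm: noncentrality 3.1 / (5.1 × √(2/43)) = 2.82, power 79.6%, equal to SAP Table 4.

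**5. If late tests become missing values (the SAP rule).** Complete-case t-test with n per arm = 96 × (1 - m) / 2. Rates above 10% are assumptions.

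| Missing at Week 49 (m) | n per arm | Non-inferiority power |
|---|---|---|
| 10% (plan) | 43.2 | 79.8% |
| 12.5% | 42.0 | 78.6% |
| 15% | 40.8 | 77.4% |
| 20% | 38.4 | 74.8% |

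The mixed model uses Weeks 13, 25 and 37 as well, so this complete-case calculation should overstate its loss.

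**6. If the protocol label were used for analysis instead.** Only comparator patients change drug. If a fraction f of their Week 49 values is taken after the switch and has gained a fraction g of the true difference, the expected difference is multiplied by 1 - f × g. Take f = 10% and g = 50%, both assumed, with 43 per arm:

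- 2.0 becomes 2.0 × 0.95 = 1.9, and power falls from 79.6% to 76.9%.
- A true difference of -1.1 becomes -1.045, and one-sided error rises from 2.5% to 2.8%.

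**The case against.** The strongest reply is that the SAP already settles the matter. It assigns visits by date and closes Week 49 before the first open-label infusion, so a post-switch FVC cannot enter the primary model as Week 49. The 10.1.8 sentence also refers to the CRF completion guidelines and can be read as a data-capture label. This stands as regards bias. A reader might infer that the comparator arm is contaminated and the non-inferiority test made anti-conservative. The planned analysis does not do that. It would happen only if the protocol label overrode Table 14.

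A reader might also infer that every make-up is either contaminated or lost. That is not so. A repeat before the first open-label infusion is a valid Week 49 value, and the protocol asks for it as soon as possible, with 45 days as the outer limit. Avalglucosidase alfa patients do not change drug, and patients with no open-label infusion do not cross over.

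Third, the loss is likely to be small. The trigger is narrow: no acceptable effort in up to eight, or a missed test. Without any make-up the value would be missing anyway. In LOTS, 57 of 60 treated patients had evaluable FVC at Month 12 (SAP 1.3.3). The mixed model keeps the patient through earlier visits under a missing-at-random assumption, and a tipping-point analysis is planned. All of this limits the size. It does not explain why the site is given an outer limit more than three times the nominal usable time, or why two governing documents assign the same primary-endpoint test to different visits.

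**Conclusion.** The point holds as a conflict between stated rules and an avoidable risk of losing primary data. For a Week 49 test due on Day 337, about 13 of the 45 permitted days (range 6 to 20) give a Week 49 value and about 31 (range 24 to 38) do not. For those later days the protocol says Week 49 and the SAP says Week 61. These counts rest only on the stated visit and infusion windows.

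Under the SAP the consequence is a missing Week 49 FVC that could have been obtained. The patient remains in the primary model but drops out of the per-protocol set and is scored as a non-responder. The number of late tests is not given, so the power and error figures are illustrations and not forecasts. The finding does not show that the primary comparison is biased. It is worth correcting because it concerns the primary endpoint and can be settled with a short timing rule.

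**What to change.** In Protocol 9.1.1 and 10.1.8, and in the site manual, add a Week 49 rule:

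- For patients continuing into the open-label phase, a repeat or late Week 49 efficacy test (including 6MWT and HHD) is done before the first open-label infusion. The infusion schedule and its windows stay as they are.
- A test after that infusion is not a Week 49 value, so the 10.1.8 labelling sentence agrees with SAP Table 14.
- For patients with no open-label infusion, keep the Table 14 limit of Day 378 and reconcile it with the 45-day rule and with Protocol 10.3.4, which asks for a test as near Week 49 as possible even outside the window.
- Keep the 45-day rule for Weeks 13, 25 and 37.

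The cost is a short addition to two protocol sections and the manual. Some repeats must be booked sooner, and a few late ones will not count as Week 49. Under Table 14 those post-switch tests already do not count.

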9.2 SECONDARY ENDPOINTS

9.2.1 Secondary efficacy endpoints

9.2.1.1 *Six-minute walk test*

The 6MWT (4) will be performed at the times specified in [Section 1.2](#) to assess functional capacity in the late-onset Pompe population. During the treatment period, the assessment will be completed before IMP infusion. See the study specific functional outcome assessment manual for further details.

The primary measurement is the distance walked in 6 minutes, measured in meters; the amount of time walked (to quantify endurance, as all patients may not complete the full 6-minute walk) will also be recorded. In addition, data will be collected for pre- versus post-test changes in heart rate. Testing equipment and administration techniques will be standardized among investigational sites. The distance (in meters) will be recorded and the corresponding percent predicted value will be calculated. Reference equations for the prediction of total distance walked applicable to the study population will be used (5, 6).

For the purpose of stabilization and if deemed necessary by the Investigator, the participant may use a walking device, such as cane or walker during the assessment. If such a device is used during the assessment, this must be recorded in the e-CRF. Also, if there is a change in device use during the trial, this must be recorded in the e-CRF.

9.2.1.2 Pulmonary function testing

Refer to [Section 9.1.1](#) on the primary efficacy endpoint for information on PFT administration.

Secondary efficacy endpoints measured by PFT will include the assessment of MIP and MEP in the upright position. Additional parameters of respiratory function collected may be analyzed as appropriate, including the assessment of FVC, MIP, and MEP in the supine position and (FEV₁) and peak expiratory flow (PEF) in the upright and supine positions.

9.2.1.3 Hand-held dynamometry (lower extremity muscle strength)

Hand-held dynamometry using the make technique will be performed at the time points specified in [Section 1.2 \(7\)](#). Equipment will be standardized across sites. During the treatment period, the assessment will be completed before IMP infusion. Stabilization procedures for all muscles groups will be followed to avoid use of compensatory muscles. To complete a make test the examiner holds the dynamometer stationary while the patient exerts a maximal force against the dynamometer. The patient makes a gradual increase in force and then completes an isometric hold for 4 to 5 seconds.

Lower extremity strength in the muscle groups detailed below will be tested by the same physical therapist or trained assessor.

- Hip Flexion;
- Hip Extension;
- Hip Abduction;
- Hip Adduction;
- Knee Flexion;
- Knee Extension;
- Ankle Dorsiflexion;
- Ankle Plantar Flexion.

The limb tests will be completed bilaterally to account for differences in the generated force for the dominant and nondominant limb. Every muscle group will be measured 2 times and the highest value will be reported in the e-CRF. Patients may use noninvasive ventilation during the dynamometry assessment. Refer to the study specific manual for instructions on test administration.

For the Canada-specific requirement regarding HHD refer to Appendix C [Section 17.3.3](#).

9.2.1.4 Quick Motor Function Test

The QMFT will be administered at the time points specified in [Section 1.2](#) to evaluate changes in motor function concurrently with the GMFM-88. During the treatment period, the assessment will be completed before IMP infusion.

The QMFT is an observer administered test comprising 16 items specifically difficult for patients with Pompe disease (8). The items are scored separately on a 5-point ordinal scale (ranging from 0 to 4) with a total score of all items ranging between 0 and 64 points. The test was validated in 91 Pompe patients, aged 5 to 76 years, with different levels of disease severity. Test administration takes approximately 10 to 15 minutes. Refer to the study specific manual for instructions on test administration.

9.2.1.5 12-Item Short-Form Health Survey (SF-12)

The SF-12 Version 2.0 will be administered at the time points specified in [Section 1.2](#). During the treatment period, the assessment will be completed before IMP infusion if possible. The SF-12 is comprised of a subset of 12 items from the SF-36 to reproduce the physical component summary (PCS) and mental component summary (MCS) scales (9). The SF-12 will be administered to assess health-related quality of life in patients ≥ 18 years of age at screening/baseline. The data from the questionnaire will be entered into the e-CRF by the site personnel.

9.2.2 Safety endpoints

9.2.2.1 Adverse events

At each study visit, patients will be evaluated for new AEs and the status of existing AEs. The Investigator may elicit symptoms using an open-ended question, followed by appropriate questions that clarify the patient's verbatim description of AEs or change in concomitant medications.

Adverse events spontaneously reported by the patient or observed by the Investigator, will be monitored throughout the study. This includes the monitoring and reporting of IARs.

Definitions of AEs, SAEs, and AESI, including reporting procedures, can be found in [Section 10.4](#) to [Section 10.7](#).

Refer to the appropriate study documentation for guidelines on the evaluation of AEs, including relationship to study treatment, severity grading, outcome, and action taken regarding the IMP.

9.2.2.2 Laboratory safety variables

The clinical laboratory data consist of blood analysis (including hematology and biochemistry) and urinalysis. Clinical laboratory values will be analyzed by a central laboratory. These values will be analyzed after conversion into standard international units, and international units will be used in all listings and tables.

Blood samples should be drawn in fasting conditions for:

- Hematology: red blood cell count, hematocrit, hemoglobin, white blood cell count with differential count (neutrophils, eosinophils, basophils, monocytes, and lymphocytes), platelets.
- Biochemistry:
 - Plasma/serum electrolytes: sodium, potassium, chloride, calcium,
 - Liver function: aspartate aminotransferase (AST), alanine aminotransferase (ALT), alkaline phosphatase, gamma-glutamyl transferase, total and conjugated bilirubin,
 - Renal function: creatinine, blood urea nitrogen, uric acid,
 - Metabolic panel: glucose, albumin, total proteins, total cholesterol, triglycerides,
 - Potential muscle toxicity: creatine kinase, creatine kinase with MB fraction, lactate dehydrogenase.

Urinalysis will include urine color, appearance, specific gravity, proteins, glucose, erythrocytes, leucocytes, ketone bodies, and pH to be assessed:

- Qualitatively: A dipstick is to be performed on a freshly voided specimen for qualitative detection using a reagent strip.
- Quantitatively: A quantitative measurement for protein, erythrocytes, and leukocytes count will be required in the event that the urine sample test is positive for any of the above parameters by urine dipstick (eg, to confirm any positive dipstick parameter by a quantitative measurement). A urine sample will be sent to the central laboratory for that purpose.

